## **Scientific Background**

The United States (US) continues to face decades-long increases in opioid overdose mortality [1]. The Centers for Disease Control and Prevention (CDC) estimates nearly 775,000 people have died of an opioid overdose since 1999 [2]. Between 2020 and 2021, overdose mortality rates involving heroin and synthetic opioids, other than methadone, increased 22%. Overall, drug overdose deaths in the US increased for all genders; all age groups over the age of 25; American Indian/Alaskan Native, non-Hispanic White, non-Hispanic Black, Hispanic, and Native Hawaiian/Pacific Islander communities; all census regions; and urban, suburban, and rural settings [3].

Opioid overdoses involve a toxic dose of natural opioids like heroin, semi-synthetic opioids like oxycodone, and/or synthetic opioids like fentanyl. Naloxone, an opioid antagonist, is an evidence-based biomedical intervention that effectively reverses opioid overdose when administered intranasally or intramuscularly [4-7]. Opioid antagonists bind to the brain's opioid receptor sites, which displaces any opioid currently in the system and temporarily negates their effects, saving the individual's life. Use of naloxone does not cause dependence or tolerance, and can, though not always, precipitate withdrawal [5-8]. Naloxone can dramatically reduce opioid overdose mortality when distributed to people likely to experience or witness an opioid overdose and packaged with education on its use, known as overdose education and naloxone distribution (OEND)[9-14].

Syringe services programs (SSPs) have a primary function of distributing safe drug use supplies, such as sterile syringes, pipes, injection-related equipment, wound care materials, etc., to facilitate the reduction of harms associated with drug use for their participants. Often, SSPs are the first to hear from their participants regarding changes in the unregulated drug market, drug use trends, and overdose experiences. Most SSPs provide a variety of other evidence-based interventions to improve the health of people who use drugs, including OEND [15-18]. SSPs reach people at high risk for experiencing or witnessing an opioid overdose, and pioneered the development of OEND [19-21]. With staff who are culturally competent in providing services for people who use opioids and pre-existing delivery systems designed to reach participants in their own environment, SSPs are an ideal venue for OEND.

Research documenting OEND's effectiveness (i.e., intervention effectiveness) for reducing opioid overdose mortality emerged over 15 years ago [7]. Only recently have studies begun to assess elements of OEND implementation effectiveness within SSPs [22-26]. As an organizational-level construct, implementation effectiveness can be defined as the aggregated consistency and quality of intervention use within an organization [27]. Findings from recent research identify factors from both the external and internal context of SSPs that shape effective implementation of OEND [22-26]. Yet, to date, no studies have assessed whether implementation strategies (i.e., approaches to improve the adoption, implementation, or sustainment of evidence-based practices) can advance implementation effectiveness of OEND within SSPs.

External facilitation-based implementation strategies have been identified as a promising approach to advance implementation outcomes [28-39]. Fundamentally, these approaches involve a person external to the organization providing interactive problem solving and support to assist implementation efforts. Often, their work is in conjunction with other implementation strategies. Whether such an approach can help SSPs, which often face substantial community, financial, and legal constraints [40], effectively implement OEND remains an important area of inquiry.

## **Study Objective**

As such, we conducted a randomized controlled trial of 105 SSPs throughout the US to understand the effectiveness of a multifaceted, external facilitation-based implementation strategy at advancing OEND implementation effectiveness within SSPs.

## **Scientific Methods**

### Trial Design

We conducted a randomized controlled trial of SSPs throughout the US and US Territories. SSPs were assigned to one of two implementation conditions using simple randomization. A standardized checklist aided this paper's clarity and transparency for describing an intervention and reporting a randomized controlled trial [41, 42]. RTI International's Institutional Review Board (IRB) approved and provided oversight for all research activities (STUDY00020448). This trial was registered at ClinicalTrials.gov as NCT03924505.

### Study Setting

The target population was operators of SSPs located throughout the US and US Territories. Prior to launching the trial, 342 SSPs were known to be operating in the US and US Territories. Described elsewhere [25], our team launched a national survey of syringe services programs (NSSSP) in February 2019 of all known SSPs operating throughout the US and its Territories, receiving a response from 263 (77%) SSPs. NSSSP responding SSPs were located in the Northeast (13%), Midwest (21%), South (24%) and West (42%) census regions. Among the responding SSPs, 247 (94%) were implementing OEND for their participants [25].

### Recruitment, Eligibility, and Enrollment

To be eligible, an organization must have: 1) met the definition of an SSP – a program which primary function is to engage people who use drugs and provide them free drug use supplies to reduce harms associated with drug use, 2) implemented OEND for a minimum of 6 months, and 3) completed the NSSSP fielded from February to July 2019. We excluded organizations such as fire departments or emergency departments of hospitals that offered drug use supply distribution since it would be an ancillary function of these organizations and OEND programs that were not part of a SSP.

A total of 243 SSPs participated in the survey and were determined to be eligible. SSPs were organized into a randomized list and were contacted sequentially for recruitment into the trial. We recruited SSPs from September 2019 to February 2021. Within that timeframe, we paused recruitment activities from March to July 2020 due to the onset of the COVID-19 pandemic. The pause in recruitment activities primarily provided an opportunity for SSPs to adapt to COVID-19 changes, particularly for their adjustment to stay-at-home orders and adoption of delivery models that minimized close person-to-person contact.

To recruit SSPs, our study team initially contacted people in leadership role(s) at each SSP via email to set up a call to explain the study and carry out enrollment activities for organizations that were interested. Organizational leadership included executive directors, program managers, and/or site coordinators. For organizations interested in participating in the trial, study staff would obtain electronic/written informed consent from the organization to join the study, carry out the organizational agreement for participation, and administer the baseline survey. Following the baseline survey, SSPs were randomized using simple randomization to two study arms: 1) dissemination of OEND best practice recommendations (i.e., Control SSPs), or 2) the Organize and Mobilize for Implementation Effectiveness (OMIE) approach along with dissemination of the OEND best practice recommendations (i.e., OMIE SSPs). Sequentially numbered sealed envelopes were used to implement the random allocation sequence, which were concealed until the point of randomization.

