#### Targeted Sample Size

The targeted sample size was estimated using PASS software [49]. We estimated that a sample of 100 SSPs (50 per arm) would provide 80% statistical power to detect a statistically significant ( $p<0.05$ ) medium effect size (Cohen's  $d = 0.45$ )[50] between study arms, assuming an

alpha of 0.05, standard deviation of 1.0 and two repeated measurements (baseline and 12-month follow-up) with a first-order autoregressive covariance structure and a correlation between observations on the same SSP of 0.3.

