#### Statistical Analysis Plan

Statistical analyses were conducted using an intent-to-treat approach. Descriptive statistics were used to summarize continuous outcomes and covariates by experimental condition; frequencies and percentages were used to summarize categorical measures. Given the varying sizes of SSPs, counts of naloxone doses and individuals receiving naloxone were summarized as a rate per number of participant contacts for syringe services in the past 3 months.

Negative binomial regression models were used to compare the number of naloxone doses distributed and contacts for naloxone refills or trainings by condition; the number of contacts for syringe services in the past 3 months was included as an offset. The model for naloxone doses was adjusted for baseline rate given the difference between conditions at baseline. The mean number of best practices adopted were compared by condition using a two-sample t-test. We also carried out a per-protocol dose response analyses, where OMIE SSPs were dichotomized at the median for the number of OMIE sessions (<10 sessions; 10+ sessions) and number of OMIE hours received (<12 hours; 12+ hours) and compared to Control SSPs. P-values <0.05 were considered statistically significant a priori. All analyses were conducted using Stata 16.1 (StataCorp LLC, Texas USA).

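### Programs enrolled before and after the COVID-19 recruitment pause are pooled with no enrolment-period term: no bias on average, but an avoidable exposure to chance imbalance and a small loss of precision, mainly in the doses model

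*Combined protocol and SAP*

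**What the plan says.** **Timing.** Recruitment, Eligibility, and Enrollment gives a window from September 2019 to February 2021 and states that "we paused recruitment activities from March to July 2020 due to the onset of the COVID-19 pandemic". The pause gave SSPs time for, among other things, "adoption of delivery models that minimized close person-to-person contact". Data Collection puts the second survey at 12 months and ends follow-up in February 2022.

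**Allocation.** Trial Design and the enrolment section both specify simple randomization. No stratification by period is mentioned.

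**Analysis.** The Statistical Analysis Plan section uses negative binomial models for the two count outcomes, where "the number of contacts for syringe services in the past 3 months was included as an offset". It does not say which visit supplies that count. The Covariates section lists contacts as a baseline survey item. Only the doses model adjusts for the baseline rate. The number of best practices is compared by a two-sample t-test. No enrolment-period or calendar-time term, stratum or sensitivity analysis appears, and enrolment period is not among the covariates.

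**The concern.** The trial spans a disruption large enough to halt its own recruitment, and that disruption falls differently on two groups of SSPs. For the first group it lies between baseline and follow-up. For the second it precedes both. A baseline rate may therefore predict follow-up differently placed on the scale in the two groups, yet the doses model gives both the same intercept and the same baseline slope.

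Nothing in the design equalises the mix of the two groups between arms. If outcomes differ by period, an uneven mix moves the estimated arm effect in this one trial, and the period differences sit in the residual variation. Readers also cannot see whether the arm effect was similar before and after the pause.

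**Working it through.** **1. The plan's own figure.** Targeted Sample Size gives "a sample of 100 SSPs (50 per arm") for 80% power at d = 0.45, with "alpha of 0.05, standard deviation of 1.0 and two repeated measurements (baseline and 12-month follow-up") and "a correlation between observations on the same SSP of 0.3". Two-sided alpha is assumed. For a time-averaged difference over two measurements the variance factor is (1 + 0.3)/2 = 0.65, so n per arm = 2 × (1.960 + 0.842)² × 0.65 / 0.45² = 50.4. Power at 50 per arm is 79.7%, so the stated figure reproduces. It describes a repeated-measures model, not the analyses in the Statistical Analysis Plan section. An analysis of follow-up adjusted for baseline has variance factor 1 − 0.3² = 0.91 and power 65.5% at 50 per arm. Step 5 uses that form because it is closest to the doses model.

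**2. Timeline from the stated dates.**

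| Cohort | Enrolled | 12-month survey | Pandemic onset falls |
|---|---|---|---|
| Before pause | Sept 2019 to about Feb 2020 | about Sept 2020 to Feb 2021 | between baseline and follow-up |
| After pause | about Aug 2020 to Feb 2021 | about Aug 2021 to Feb 2022 | before both |

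Follow-up is after onset in both cohorts. The difference lies in the baseline.

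**3. Chance imbalance.** The documents do not give the number enrolled before the pause. Uniform recruitment over 6 + 7 open months would give 6/13 = 46%. A range of 30% to 70% is assumed. The between-arm difference in pre-pause share has mean 0 and SD of about 2 × √(f(1 − f)/105). Simulating simple randomization of 105 SSPs gives:

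| Pre-pause share f (assumed) | SD of difference | Difference > 10 points | Difference > 15 points |
|---|---|---|---|
| 30% | 0.091 | 28% | 10% |
| 46% | 0.098 | 30% | 13% |
| 50% | 0.099 | 33% | 12% |
| 70% | 0.090 | 27% | 10% |

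**4. Effect of an imbalance on a rate ratio.** If the follow-up rate differs between cohorts by ratio r (assumed), an imbalance D multiplies the unadjusted rate ratio by about exp(|ln r| × D). At f = 46% the 97.5th percentile of D is about 0.19. The multiplier is then 1.02 for r = 0.9, 1.07 for r = 0.7 and 1.14 for r = 0.5. The average over allocations is 1.00.

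**5. Precision in a baseline-adjusted model.** Suppose the cohorts' baselines differ by s SD, their follow-ups do not, and half the SSPs are in each (all assumed). Without a period term the residual variance is 1 − ρ²/(1 + s²/4). With it, the residual variance is 1 − ρ². Power at d = 0.45 and 50 per arm:

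| ρ | s | Without term | With term | Gain (points) |
|---|---|---|---|---|
| 0.3 (plan) | 0.3 | 65.4% | 65.5% | 0.1 |
| 0.3 (plan) | 1.0 | 64.6% | 65.5% | 0.9 |
| 0.6 (assumed) | 0.3 | 79.8% | 80.3% | 0.5 |
| 0.6 (assumed) | 1.0 | 76.0% | 80.3% | 4.3 |

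**6. Negative binomial simulation.** Settings, all assumed: 105 SSPs, 46% pre-pause, baseline-rate adjustment, follow-up contacts as offset, 400 trials per scenario. With a true log rate ratio of 0.45, rejection without and with the term was 67.0% and 66.8% with no cohort change in contacts, 67.2% and 67.8% with early-cohort contacts at 0.7 of baseline, and 68.2% and 72.0% at 0.5. With no true effect, the rates at 0.7 and 0.5 were 10.0% against 9.0% and 9.2% against 9.0%. The excess over 5% reflects model-based standard errors under these settings and was there either way.

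**The case against.** **No bias is at issue.** Both arms were enrolled concurrently, so leaving out the period term does not bias the comparison on average. This stands, and it makes the point one of precision and chance imbalance only.

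**A reader might infer that the pandemic changed the contact denominator in the first cohort.** The documents do not support that. The enrolment section's wording concerns physical proximity in delivery. The offset counts service encounters. No encounter counts, direction or size of change are given, and the second cohort's 12 months also fell within the pandemic, so change there is not excluded.

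**A reader might also infer that all three primary analyses are affected in the same way.** They are not. Only the doses model has a baseline slope. The other count model is touched by the baseline-to-follow-up difference only if its offset is baseline contacts, which the plan leaves open. Best practices has no denominator and no baseline term, so the case there rests only on general period variation and chance imbalance.

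**Large gains can be computed, but only by assumption.** If the cohorts' follow-up means differed by 0.5 to 1.0 SD, power of the best-practices t-test would rise from 61% to between 63% and 70% with adjustment. Nothing in the documents implies a gap of that size between two follow-ups that both post-date onset, so these figures should carry no weight.

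**The design gives some protection.** SSPs were approached in random order, which limits cohort differences other than calendar time, and the pause let programs adapt first. This is fair, but it does not balance period between arms.

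**Conclusion.** The point holds as a small, nearly free improvement centred on the doses model. The documents establish the two cohorts, the simple randomization and the absence of a period term. They do not establish bias, a change in contact counts, or a need for a period-by-baseline interaction.

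Size: an imbalance of more than 10 points has roughly a 27% to 33% chance. An imbalance near the upper 2.5% limit would multiply a rate ratio by about 1.02 to 1.14 for assumed cohort rate ratios of 0.9 to 0.5. The power gain runs from under 1 point at the plan's correlation to about 4 points under favourable assumptions. All of this depends on the assumed pre-pause share and cohort differences, which the documents do not report. In the checks the term cost essentially nothing: 0.2 points in the simulation with no cohort change, well within simulation error.

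**What to change.** - Add one indicator, enrolled before or after the March to July 2020 pause, to the doses model. No interaction with baseline is needed.
- Use the same indicator in the other two primary analyses, as a covariate or a labelled sensitivity analysis. For best practices this means a linear model in place of the t-test.
- Report the number of SSPs by arm and period, and the arm effect by period as description only.
- State which visit's contacts form the offset.

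The plan describes its analyses as already conducted. Where results are final, present the adjusted analyses as post hoc sensitivity analyses. The cost is about one degree of freedom per model and a sentence or two in the SAP. The indicator needs only enrolment dates, which the study team should hold.

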#### Covariates

The baseline survey also collected information on region of operation, the number of staff and volunteers at the SSP, staff training in OEND, the prior year's annual budget in dollars, the number of participant contacts at the SSP in the past 3 months.

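### Baseline adjustment is applied to one of three primary outcomes, and because an arm difference was seen; one fixed rule for all three would be consistent and would recover some precision

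*Combined protocol and SAP*

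**What the plan says.** **Allocation.** Recruitment, Eligibility, and Enrollment says that, after the baseline survey, "SSPs were randomized using simple randomization to two study arms". No strata, blocks or minimisation are described. Study Objective gives 105 SSPs.

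**Baseline data.** The Covariates section lists "region of operation, the number of staff and volunteers at the SSP, staff training in OEND, the prior year's annual budget in dollars", and also "the number of participant contacts at the SSP in the past 3 months". Data Collection describes a survey at baseline and again at 12 months. Targeted Sample Size assumes two measurements per SSP with a correlation of 0.3.

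**Analysis of the three primary outcomes (Statistical Analysis Plan).**
- Naloxone doses: negative binomial model with syringe-service contacts as offset. "The model for naloxone doses was adjusted for baseline rate given the difference between conditions at baseline".
- Participants receiving naloxone: negative binomial model with the same offset and no baseline term. The section describes this outcome as contacts for refills or trainings; I take it to be the second primary outcome named under Trial Outcomes.
- Best practices: two-sample t-test with no covariates.

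Region, staff, training and budget appear in none of the three analyses.

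**The concern.** Which covariates to adjust for should follow from what is expected to predict the outcome, and should be settled without looking at the arms. Here the stated reason for the one adjustment is a difference that was seen. The other two primary outcomes are treated differently, and no reason is given beyond that. A reader cannot tell what rule would have applied had the differences fallen elsewhere.

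The second loss is precision. SSPs differ in size, as the plan itself acknowledges when it turns counts into rates. A baseline measurement of the outcome, where one exists, is usually the most useful covariate available. The sample size calculation relies on two correlated measurements per SSP, yet the best-practices test as described makes no use of the first.

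**Working it through.** **Inputs.** From Targeted Sample Size: d = 0.45, SD 1.0, alpha 0.05 (two-sided assumed, as sidedness is not stated), 50 per arm, two measurements, correlation 0.3, 80% power. From Study Objective: 105 SSPs. The share of outcome variance explained by covariates (R²) is not in the documents. Only 0.3² = 0.09 can be derived from them; 20% and 30% are assumptions.

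**1. The plan's own figure.** For the average of two measurements with correlation 0.3, the SD is √((1 + 0.3)/2) = 0.806. At d = 0.45 this needs 51 per arm, and 50 per arm gives power 0.797 (0.789 with the noncentral t). The stated 50 per arm and 80% therefore reproduce, but only for a comparison that uses both measurements.

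**2. The best-practices test as described.** A two-sample t-test on one measurement has SD 1.0. Noncentral-t power at 50 per arm is 0.606, or 61%. The gap between 80% and 61% arises because the sample size calculation and the test differ. Simple randomisation did not cause it.

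**3. With adjustment.** The residual SD is √(1 − R²), and the effective standardised difference is 0.45/√(1 − R²).

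| R² | Source | Residual SD | Effective d | Power, 50 per arm |
|---|---|---|---|---|
| 0 | t-test as described | 1.000 | 0.450 | 61% |
| 0.09 | plan's correlation, 0.3² | 0.954 | 0.472 | 65% |
| 0.20 | assumed | 0.894 | 0.503 | 70% |
| 0.30 | assumed | 0.837 | 0.538 | 76% |

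**4. Price of the covariates.** The best-practices model would carry one baseline value, three region indicators and one size term, so q = 5. Under unstratified allocation, estimating q coefficients inflates the variance of the treatment effect by about 1 + q/(N − q − 3). With N = 100 this is 1 + 5/92 = 1.054.
- With this inflation, and degrees of freedom reduced from 98 to 93, power is about 68% at R² = 0.20 and 74% at R² = 0.30.
- For the baseline value alone (q = 1, R² = 0.09) the inflation is 1 + 1/96 = 1.010 and power is 64%.
- With five terms the variance breaks even where (1 − R²) × 1.054 = 1, that is, R² of about 5%.

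**5. What simple randomisation does and does not do.** With 105 SSPs the SD of a standardised covariate difference is 2/√105 = 0.195. The chance that one given covariate differs by more than 0.3 SD is therefore 12%. Some imbalance is expected, and the standard error of the unadjusted test already allows for it. A 60/45 split in arm size or worse has probability 17%, but a 60/45 split raises the variance by only (1/60 + 1/45)/(4/105) − 1 = 2%.

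**The case against.** **The allocation is sound.** Simple randomisation of about 100 units, with concealed sequential envelopes, is a legitimate choice. Chance imbalance is not bias, and the unadjusted tests keep their type I error. This stands. A reader might infer that the method of allocation invalidates the comparison; the documents do not support that.

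**Size is not ignored.** Contacts are the offset in both count models, so two of the three primary outcomes are already analysed per contact. This stands too. For size, the gap is confined to best practices. Adding log contacts to a model that already has contacts as offset would free the coefficient fixed at 1 and change the meaning of the rate ratio, so the fix avoids it.

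**The baseline difference need not come from region or size.** It is tempting to say that it arose because allocation ignored them. The SAP describes a difference in a rate already divided by contacts, and nothing links it to region or size or shows that stratifying would have prevented it.

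**Joint imbalance figures overstate.** Chances of 33% (three covariates) or 48% (five) that at least one differs by more than 0.3 SD follow from 1 − (1 − 0.124)^k, but only if the covariates are independent. Staff, budget and contacts plausibly all track size. I do not rely on these figures.

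**The choice may have been innocent.** The Masking section says that the statistician was blinded to condition throughout. It would be wrong to infer that the adjustment was picked to favour an arm. Blinding does not, however, supply a rule for treating three primary outcomes differently.

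**The gain is uncertain.** Power for best practices depends on R², which the documents do not give beyond the assumed correlation, and no gain is calculated for the count models. This stands, and it limits how strongly the point can be put.

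**Conclusion.** The point holds as a matter of consistency and precision, not validity. Baseline adjustment was applied to one primary outcome of three, for a reason seen in the data. Region, staff, training and budget go unused throughout, and size is unused for best practices.

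The quantified cost concerns best practices only. Power at d = 0.45 and 50 per arm is 61% as described. Before the small price of the added terms, it is about 65% if the plan's correlation of 0.3 applies to this outcome, and 70% or 76% if R² is 20% or 30%. After that price the figures are about 64%, 68% and 74%, the first for baseline adjustment alone. If all five terms together explain less than about 5% of the variance, nothing is gained. These figures assume a two-sided test, approximately normal outcomes, and that the number of best practices was recorded at baseline, which the documents imply but do not itemise.

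**What to change.** Apply one rule to all three primary outcomes, not chosen from observed arm differences:

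1. **Both negative binomial models:** adjust for the baseline rate of the outcome and for census region. Keep contacts as the offset, and state whether those contacts are from baseline or month 12, since month-12 contacts would be post-randomisation.
2. **Best practices:** replace the t-test with a linear model containing condition, the baseline number of best practices (if recorded), census region and log baseline contacts. Name that size measure in the text instead of leaving a choice of several.
3. **Reporting:** the analyses are described in the past tense, so present these results beside the existing ones and label them post hoc. They cannot now be called prespecified.

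No change to the allocation is proposed; it is complete. The cost is a reanalysis of data that the plan says, or implies, were collected, and about five degrees of freedom in the best-practices model (four in each count model: one baseline term and three for region).
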